9.1.2 Handling of Missing Data

This is a prospective pilot study and therefore we do not anticipate any missing data. In the event of any unexpected missing data, no attempt to impute this missing data will be made; missing data will simply be treated as missing in the statistical analysis, and replacement participants will be enrolled to achieve the target accrual of n=170 participants.

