7.4 Early Withdrawal of Subjects

7.4.1 When and How to Withdraw Subjects

Patients are free to withdraw at any time and for whatever reason. If patient withdraws consent prior to arrival to operating room, the study data will not be collected. If patient withdraws consent after study data was already completed, the participant will need to provide instructions to the study team to remove his/her data from the data set. Pre-specified reasons for discontinuing include, but are not limited to, the following:

- Patient Request: Patient decided that he/she did not want to continue (for any reason)
- Adverse Event: Patient experienced a related or unrelated event that would interfere with the study objectives/evaluation
- Inclusion/Exclusion Discrepancy/Violation: Patient should not have been enrolled
- Other: Any other reason

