8.4 Masking/Blinding of Study

This is an open-label pilot investigation. Masking and blinding procedures are not applicable.

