9.1 Sample Size Determination

Based on preliminary data, intubating score of 3 (ideal conditions) will occur in approximately 65% of patients in the two-minute group. With a sample size of 83 patients per group (166 patients total), we will have 80% power at the 5% significance level to detect a difference in this outcome of 20% (i.e. 65% vs. 85%) between the two-minute group and the other two treatment groups using a chi-square test. We will enroll 85 patients in each group (170 total) to account for possible dropouts.

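### Randomised patients who end without a complete intubation score are dropped and replaced, and the analysis set is defined by what happens after allocation rather than by randomisation

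*Combined protocol and SAP*

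**What the plan says.** Four provisions act together.

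- **Missing data and replacement (9.1.2).** No missing data are expected and none will be imputed: "missing data will simply be treated as missing in the statistical analysis, and replacement participants will be enrolled to achieve the target accrual" of 170. The section sets no cap on replacement, does not say which arm a replacement joins, and does not ask for losses to be compared by arm.
- **Discontinuation (7.4.1).** The listed reasons include an adverse event ("Patient experienced a related or unrelated event that would interfere with the study objectives/evaluation"), an eligibility finding ("Inclusion/Exclusion Discrepancy/Violation: Patient should not have been enrolled") and an open category for anything else. The section gives no timing relative to allocation.
- **Analysis set (9.2).** The primary analysis takes participants who go through surgery and complete monitoring of residual blockade, whether or not they withdraw. A secondary analysis leaves out those who withdrew. No section defines a set of all randomised patients.
- **Masking (8.4).** "This is an open-label pilot investigation"

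Section 9.1 already adds patients for losses: "We will enroll 85 patients in each group (170 total) to account for possible dropouts".

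**The concern.** Randomisation protects the comparison only if the patients analysed are the patients allocated. Under these provisions a patient can be allocated, end without all three items scored, be treated as missing and be succeeded by a new enrolee. The people who decide on discontinuation know the arm. Participation lasts about 15 minutes around intubation (6.3), so an event that interferes with evaluation could also be a sign of poor intubating conditions.

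If such losses are more common under one trigger, that arm sheds patients who would not have scored 3, and its ideal rate is overstated. The error can go either way: a false difference if the losses fall in one of two equal arms, or a diluted true difference if they fall in the worse arm. Full arms of 85 in the final table would give no hint of it unless losses are tabulated by arm.

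**Working it through.** **1. Inputs from section 9.1.** The plan expects that an "intubating score of 3 (ideal conditions) will occur in approximately 65% of patients in the two-minute group", with 85% as the alternative, 80% power, 5% significance, a chi-square test, 83 per group, and 85 enrolled per group. Sidedness is not stated and is taken as two-sided.

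**2. The plan's own figure.** With p1 = 0.65, p2 = 0.85 and mean 0.75:

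n = [1.96·√(2·0.75·0.25) + 0.842·√(0.65·0.35 + 0.85·0.15)]² / 0.20² = 72.4, so 73 per group without continuity correction.

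With the correction, (n/4)·[1 + √(1 + 4/(n·0.20))]² = 82.1, so 83 per group. The stated 83 reproduces. The dropout allowance is 170 − 166 = 4 patients, two per arm, or 4/170 = 2.4%. The sample size is not in question.

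**3. Who is exposed.** Setting 7.4.1, 8.2, 9.1.2 and 9.2 side by side:

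- Withdrawn, but went through surgery and completed monitoring: kept by 9.2.
- Conditions unacceptable at the trigger: 8.2 leads to a later laryngoscopy, not to exit from the study.
- Allocated, but ends without a complete score for any reason: treated as missing and replaced under 9.1.2. Nothing in 9.2 brings this patient back.

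Only the third row is open. Incomplete scores are possible because 8.2 collects the laryngoscopy rating afterwards with no deadline.

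**4. Size, under assumed losses.** The documents give no number of such losses, so 2, 4 or 6 per 85 allocated is an assumption. Suppose both arms are truly at 65%, and k non-ideal patients per 85 are lost from one arm only. Replacements pass through the same filter, so the observed rate in that arm is 0.65·85/(85 − k) = 55.25/(85 − k). False-positive rates come from exact binomial enumeration of the two-sided test with 85 per arm.

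| k lost, one arm | Observed rate | False positive, uncorrected | False positive, corrected |
|---|---|---|---|
| 0 | 65.0% | 4.8% | 3.3% |
| 2 | 66.6% | 5.4% | 3.8% |
| 4 | 68.2% | 7.1% | 5.1% |
| 6 | 69.9% | 10.4% | 7.8% |

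In the other direction, with true rates of 65% and 85% and the same losses in the two-minute arm, power falls from 86.8% to 81.6%, 74.9% and 66.6% (uncorrected), or from 82.0% to 75.7%, 67.9% and 58.7% (corrected).

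**5. What replacement adds.** Dropping the patients is enough to shift the rate. Without replacement, k = 6 leaves 79 in that arm with the same expected rate of 69.9%, and the same enumeration gives false-positive rates of 10.4% and 7.5%. Replacement keeps the shift in place and restores the arm to full size. Deleting replacement is therefore necessary but not sufficient; the analysis set and the handling of incomplete scores must change too.

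**The case against.** The strongest reply is that very few patients can leave this way. Section 9.2 keeps withdrawn patients who complete surgery and monitoring. Poor conditions are what the scale is built to record. An independent observer notes two of the three items (8.2), so those do not wait for the later survey. The patient is anaesthetised and cannot ask to stop during the key minutes. Losing 2, 4 or 6 of the roughly 30 non-ideal patients expected in an arm (0.35·85 = 29.75) means that 7%, 13% or 20% of them go unscored, and nothing in the documents supports such rates. Section 11.3 also promises that missing data will be explained. Having both a dropout allowance and replacement is redundant rather than contradictory.

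Most of this stands, and it limits the size of the problem. It does not remove it. The entry condition in 9.2 lies after randomisation, and it names residual blockade rather than intubating conditions. The observer's items help only if the plan says how an incomplete score is classified, and it does not. Explaining missing data is not the same as reporting it by arm.

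A reader might infer that the plan lets the team remove the worst intubations from an arm at will. The documents do not support that: discontinuation alone does not take a patient out of the analysis, and 7.4.1 is silent on timing rather than directed at the period after allocation.

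**Conclusion.** The point holds in a limited form. The plan drops and replaces randomised patients who have no complete score and defines no all-randomised set, so in an open-label trial the analysed arms can differ from the allocated arms for reasons related to outcome. The bias is possible, not shown. It depends on the number of such losses, on their being non-ideal patients, and on their being unequal between arms.

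At two losses in one arm the effect is negligible. At four, the false-positive rate is 7.1% uncorrected and about the nominal 5% with continuity correction. At six it is clearly above nominal under either version. Loss of power, if the losses fall in the two-minute arm, appears sooner. The repair is cheap and should be made before enrolment. The sample size calculation itself is sound.

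**What to change.** - **9.2:** define the primary set as all randomised patients, analysed in the arm to which they were allocated. Remove the condition about monitoring of residual blockade.
- **9.1.2:** delete replacement of patients after allocation; 9.1 has already raised 166 to 170 for dropouts.
- **9.1.2, partial scores:** where any recorded item is above 1, classify the patient as not score 3 even if another item is missing. A total of 3 is then impossible, so no imputation is involved.
- **7.4.1:** base eligibility exclusions from analysis only on facts recorded before allocation. State that discontinuation for an adverse event does not end collection of the intubation score.
- **Reporting:** tabulate missing scores by arm and reason, and add a sensitivity analysis counting every missing score as not score 3. Keep this as a sensitivity analysis, because some losses will have nothing to do with intubating conditions.

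The cost is wording, plus administrative losses beyond two per arm that are no longer replaced. By the same enumeration, 81 scored patients per arm give 84.9% power uncorrected and 80.1% corrected, against 86.8% and 82.0% at 85. The sensitivity analysis has less power: if 2% of scores are missing in both arms regardless of outcome, 83.8% uncorrected and 78.7% corrected; at 5%, 79.2% and 73.8%. No change to clinical management is proposed.

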9.2 Subject Population(s) for Analysis

Each participant who goes through the surgery and completes monitoring of residual neuromuscular blockade will be included in the primary analysis regardless of study withdrawal for any reason. In the event of any study withdrawals, in secondary analysis we will examine the sensitivity of our results to the exclusion of patients who withdrew.

10 Safety and Adverse Events

10.1 Definitions

10.1.1 Unanticipated Problems Involving Risk to Subjects or Others (UPIRTSO)

Any unanticipated problem or adverse event that meets the following three criteria:

- Serious: Serious problems or events that results in significant harm, (which may be physical, psychological, financial, social, economic, or legal) or increased risk for the subject or others (including individuals who are not research subjects). These include: (1) death; (2) life threatening adverse experience; (3) hospitalization - inpatient, new, or prolonged; (4) disability/incapacity - persistent or significant; (5) birth defect/anomaly; (6) breach of confidentiality and (7) other problems, events, or new information (i.e. publications, DSMB reports, interim findings, product labeling change) that in the opinion of the local investigator may adversely affect the rights, safety, or welfare of the subjects or others, or substantially compromise the research data, **AND**
- Unanticipated: (i.e. unexpected) problems or events are those that are not already described as potential risks in the protocol, consent document, or not part of an underlying disease. A problem or event is "unanticipated" when it was unforeseeable at the time of its occurrence. A problem or event is "unanticipated" when it occurs at an increased frequency or at an increased severity than expected, **AND**
- Related: A problem or event is "related" if it is possibly related to the research procedures.

10.1.2 Adverse Event

An untoward or undesirable experience associated with the use of a medical product (i.e. drug, device, biologic) in a patient or research subject.

10.1.3 Serious Adverse Event

Adverse events are classified as serious or non-serious. Serious problems/events can be well defined and include;

- death
- life threatening adverse experience
- hospitalization
- inpatient, new, or prolonged; disability/incapacity
- persistent or significant disability or incapacity
- birth defect/anomaly

and/or per protocol may be problems/events that in the opinion of the sponsor-investigator may have adversely affected the rights, safety, or welfare of the subjects or others, or substantially compromised the research data.

All adverse events that do not meet any of the criteria for serious, should be regarded as **non-serious adverse events**.

10.1.4 Adverse Event Reporting Period

For this study, the follow-up period is defined as up to successful intubation.

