4.3 Risks and Benefits

- Utilization of quantitative neuromuscular monitors is currently standard of care at Mayo Clinic. However, most providers place these devices after induction of anesthesia. Placing them prior to induction ensures they are working appropriately throughout the perioperative experience.
- Intubating the trachea at a TOFC=1 could result in conditions that suboptimal with movement of the vocal cords. However, the current standard of care involves intubating once about two minutes has elapsed and movement of the vocal cords is commonly seen. Whether the TOFC=1 or two minutes has elapsed, endotracheal intubation carries the risk of damage to the vocal cords. Utilization of the TOFC=1 represents a potential benefit to the patient as providers will have to use a quantitative neuromuscular monitor to determine intubation timing, rather than just intubating based on unclear, subjective endpoints.

5 Study Objectives

Primary Objective

Compare intubating conditions when patients are intubated at 2 different endpoints: TOFC=1 or 2 minutes after administration of rocuronium at 0.6 mg/kg (usual current clinical routine).

Secondary Objective

Correlate the ratio of the amplitude of the first twitch and control twitch (T_1/T_c) to intubating conditions.

6 Study Design

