6.3 Duration of Participation

15 min at the start of the operation

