8.5 Schedule of Events

Schedule of Events		
Study Activity	Visit 1	Visit 2
Scheduled Intubation		X
Intubating conditions observation		X
Informed consent	X	
Review of Medical Record	X	
Adverse event evaluation		X

9 Statistical Plan

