10.1.6 Post-study Adverse Event

All unresolved adverse events should be followed by the sponsor-investigator until the events are resolved, the subject is lost to follow-up, or the adverse event is otherwise explained. At the last scheduled visit, the sponsor-investigator should instruct each subject to report, to the sponsor-investigator, any subsequent event(s) that the subject, or the subject's personal physician, believes might reasonably be related to participation in this study.

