10.2 Recording of Adverse Events

At each contact with the subject, the study team must seek information on adverse events by specific questioning and, as appropriate, by examination. Information on all adverse events should be recorded immediately in the source document, and also in the appropriate adverse event section of the electronic case report form (CRF). All clearly related signs, symptoms, and abnormal diagnostic, laboratory or procedure results should be recorded in the source document.

All adverse events occurring during the study period must be recorded. The clinical course of each event should be followed until resolution, stabilization, or until it has been ultimately determined that the study treatment or participation is not the probable cause. Serious adverse events that are still ongoing at the end of the study period must be followed up, to determine the final outcome. Any serious adverse event that occurs during the Adverse Event Reporting Period and is considered to be at least possibly related to the study treatment or study participation should be recorded and reported immediately.

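### Section 10.3.1 both requires and excludes IRB reporting of a possibly related UPIRTSO, and the adverse-event period ends at intubation with no active collection scheduled afterwards

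*Combined protocol and SAP*

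**What the plan says.** **Reporting to the IRB.** Section 10.1.1 sets three conditions for a UPIRTSO: serious, unanticipated and related. A possible relation to the research procedures satisfies the third. Section 10.3.1 first commits the sponsor-investigator to report UPIRTSOs and Non-UPIRTSOs in line with institutional IRB policy. It then requires any SAE that the principal investigator has determined to be a UPIRTSO to reach the IRB within 5 working days. Its closing sentence restricts IRB reporting, for this protocol, to SAEs and UPIRTSOs that are directly related. Section 10.2 uses another threshold for immediate recording and reporting: "Any serious adverse event that occurs during the Adverse Event Reporting Period and is considered to be at least possibly related" to study treatment or participation.

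**Reporting period.** Section 10.1.4 reads: "For this study, the follow-up period is defined as up to successful intubation". Section 4.3 says: "Whether the TOFC=1 or two minutes has elapsed, endotracheal intubation carries the risk of damage to the vocal cords". The schedule in 8.5 marks "Adverse event evaluation" at Visit 2, which 8.2 heads as the day of surgery. Section 10.2 adds: "All adverse events occurring during the study period must be recorded". It also requires questioning about adverse events at every contact. Section 10.1.6 has unresolved events followed up and asks subjects to report later events that they or their physician "believes might reasonably be related to participation in this study".

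**Causality.** The worksheet in 10.3.1 asks for the relationship to the research device, and all five grades of the Relationship Index refer to a device. Sections 8.2 and 8.3 randomise the timing of intubation.

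**The concern.** An investigator facing a serious, unanticipated, possibly related event cannot comply with both the 5-working-day sentence and the closing sentence of 10.3.1. Whether the IRB hears of the event would depend on which sentence is read.

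The reporting period raises a different problem. The one procedural injury that the protocol names is caused by passing the tube, and the stated period ends when the tube is in. Harm noticed later falls outside it. The immediate-reporting rule for SAEs in 10.2 is tied to the same period. A published statement that no airway injury occurred could then reflect only that nobody looked.

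The form adds a smaller gap. An event attributed to when the patient was intubated has no field in which that judgement can be graded.

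**Working it through.** No arithmetic bears on the main points; the check is a comparison of the texts.

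**1. One event under each IRB rule.** Take an SAE that is serious and unanticipated, and that the investigator judges possibly, but no more than possibly, related to the research procedures.

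| Place | Standard | Result |
|---|---|---|
| 10.1.1 | possibly related to research procedures | it is a UPIRTSO |
| 10.3.1, opening sentence | UPIRTSOs, in line with IRB policy | reportable, subject to a policy not in the documents |
| 10.3.1, 5-working-day sentence | any SAE determined to be a UPIRTSO | reportable, no further qualifier |
| 10.3.1, closing sentence | directly related only | not reportable |

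The second and fourth rows could perhaps be reconciled through the policy. The third and fourth cannot. The Relationship Index does not help: its grades are not related, unlikely, possible, probable and definite, so nothing on the form defines directly related.

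**2. Where post-intubation injury would be picked up.**

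- 10.1.4: the period has ended.
- 8.5 with 8.2: evaluation belongs to a day-of-surgery visit, which is wider than 10.1.4, but no time of day or assessment after surgery is given.
- 10.2, all events: applies to a study period that is not defined.
- 10.2, questioning at each contact: an active rule, but only Visits 1 and 2 are scheduled and no post-operative contact is listed.
- 10.1.6: covers events already detected, plus self-report. The latter is passive.
- 10.4: calls for a data and safety monitoring plan. The text in 12.1 contains no adverse-event check.
- 17.1: records cord position and the reaction to tube insertion and cuff inflation. These describe intubating conditions, not injury noticed later.

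The end of collection is therefore stated inconsistently, and no provision schedules an active look after the tube is placed.

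**3. Causality field.** Sections 10.1.1 and 10.2 require a judgement of relatedness to research procedures, or to study treatment or participation. The worksheet and index provide a grade for the device only. The device is not named there. By inference it is the TetraGraph, which 8.2 places in every patient.

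**4. Cost of a chart review.** The 170 participants come from 6.2; the minutes per chart are an assumption. Hours = 170 × minutes / 60.

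- 2 minutes: 170 × 2 / 60 = 5.7 h
- 5 minutes: 170 × 5 / 60 = 14.2 h
- 10 minutes: 170 × 10 / 60 = 28.3 h

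**The case against.** **The IRB policy may settle the reporting rule.** The opening sentence of 10.3.1 defers to it, and we cannot see it. The closing sentence may also have been meant loosely, with directly related standing for related in the sense of 10.1.1. Either is possible. But the 5-working-day sentence carries no qualifier and the closing sentence is expressly specific to this protocol, so the contradiction stands as written.

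**Collection after intubation may be wider than 10.1.4 suggests.** A reader might infer from 6.3 ("15 min at the start of the operation") that adverse events stop being collected 15 minutes into surgery at the latest. The documents do not support that cap: 8.5 and 8.2 put the evaluation at a day-of-surgery visit, and the study period in 10.2 has no stated end. A separate monitoring plan under 10.4 may also exist. What remains is an inconsistency, and the absence of any scheduled post-operative contact.

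**Cord damage would not ordinarily be a UPIRTSO.** This is right. Section 4.3 describes it as a risk, so under 10.1.1 it is anticipated unless it is more frequent or severe than expected. A reader might join the points and infer that cord injuries would go unreported because of 10.3.1. That chain does not follow, and the two points are independent.

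**The device grade may be enough.** In the TOFC=1 arm the monitor reading triggers intubation, so a device grade can arguably cover timing there. It does not clearly do so in the two-minute arm. Relatedness to procedures must still be judged in both arms; it is ungraded on the form, not unassessed. That is why this part is minor.

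**The stakes for the trial's result are low.** This also stands. No adverse-event comparison is planned.

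**Conclusion.** The point holds in three parts of unequal weight.

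1. **Wrong as written, and the firmest part:** 10.1.1 and the 5-working-day sentence of 10.3.1 make a possibly related SAE that is a UPIRTSO reportable, and the last sentence of 10.3.1 excludes it.
2. **Should be changed:** 10.1.4 closes the reporting period at successful intubation for all 170 participants, in tension with 8.5, 8.2 and 10.2. Injury first noticed afterwards is not actively collected. This assumes that no separate monitoring plan schedules such a check; none is shown.
3. **Minor:** the form lacks a causality grade for study procedures, including assigned timing.

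A reader might infer that the arms differ in harm, or that the gap hides such a difference. The documents do not support that. Section 4.3 names the risk in both arms and says of usual practice that "the current standard of care involves intubating once about two minutes has elapsed and movement of the vocal cords is commonly seen". They give no injury rate, so the number of missed events cannot be estimated. The primary endpoint and sample size are unaffected.

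**What to change.** 1. Delete or rewrite the last sentence of 10.3.1 so that 10.1.1, 10.2 and 10.3.1 apply one relatedness standard, expressed in Relationship Index grades and consistent with the cited IRB policy.
2. Reconcile 10.1.4 with 8.5, 8.2 and 10.2 so that the reporting period runs past intubation, and define the study period. The investigators should choose and state the end point, since the documents give no basis for a particular one. Collect airway events from the EHR, already a data source under 11.3, and list them descriptively by arm. Such a review finds only what is charted. If the present window is kept, state that harm after intubation was not actively collected and draw no safety conclusion about it.
3. Add to the worksheet and index a grade for relationship to study procedures, including assigned intubation timing, beside the device grade.

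The cost is one IRB amendment under section 13, possibly an update to the consent or privacy authorization (11.1), and roughly 6 to 28 hours of chart review on the assumption above, in a study that 14.1 describes as unfunded. Parts 1 and 3 are wording changes and can go in the same amendment.
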